13.11.8. Safety Tables

Safety: Tables					
No.	Population	IDSL / Example Shell	Title	Programming Notes	Deliverable [Priority]
Adverse Events (AEs)					
3.1.	Safety	AE1	Summary of Treatment Emergent Adverse Events by System Organ Class and Preferred Term		EOT, SAC
3.2.	Safety	AE1	Summary of Post-Treatment Adverse Events by System Organ Class and Preferred Term		SAC
3.3.	Safety	AE3	Summary of Common (>=5%) Treatment Emergent Adverse Events by Overall Frequency		EOT, SAC
3.4.	Safety	AE1	Summary of Drug-Related Treatment Emergent Adverse Events by System Organ Class and Preferred Term		EOT, SAC
3.5.	Safety	AE15	Summary of Common (>=5%) Non-serious Treatment Emergent Adverse Events by System Organ Class and Preferred Term (Number of Participant and Occurrences)		SAC
3.6.	Safety	AE5A	Summary of All Adverse Events by Maximum Intensity by System Organ Class and Preferred Term		SAC

Safety: Tables					
No.	Population	IDSL / Example Shell	Title	Programming Notes	Deliverable [Priority]
3.7.	Safety	AE1	Summary of Treatment Emergent Adverse Events for Participants with Absolute Neutrophil Count Below Lower Value of PCI		SAC
Serious and Other Significant Adverse Events					
3.8.	Safety	AE16	Summary of Serious Treatment Emergent Adverse Events by System Organ Class and Preferred Term (Number of Participants and Occurrences)		EOT, SAC
3.9.	Safety	AE16	Summary of Fatal Serious Treatment Emergent Adverse Events by System Organ Class and Preferred Term (Number of Participants and Occurrences)	Only with subcategory: Number of Fatal SAEs	EOT, SAC
3.10.	Safety	AE1	Summary of Serious Treatment Emergent Drug-related Adverse Events by System Organ Class and Preferred Term		SAC
3.11.	Safety	AE1	Summary of Adverse Events Leading to Permanent Discontinuation of Study Treatment or Withdrawal from Study by System Organ Class and Preferred Term		EOT, SAC
3.12.	Safety	AE1	Summary of Post-treatment Serious Adverse Events by System Organ Class and Preferred Term		SAC
3.13.	Safety	AE1	Summary of Treatment Emergent Adverse Events of Special Interest by Lower Level Term		EOT, SAC
3.14.	Safety	AE1	Summary of Treatment Emergent Adverse Events of Special Interest by System Organ Class and Preferred Term		EOT, SAC
3.15.	Safety	Example 17	Summary of Post-Inhalation Cough by Visit		EOT, SAC
3.16.	Safety	Example 28	Summary of Post-Inhalation Cough by Visit and Cough Type		EOT, SAC
3.17.	Safety	Example 33	Summary of Post-Inhalation (PI) Cough at Any Visit		EOT, SAC

Safety: Tables					
No.	Population	IDSL / Example Shell	Title	Programming Notes	Deliverable [Priority]
Laboratory: Chemistry					
3.18.	Safety	LB1	Summary of Chemistry Data	For EOT summarise Alkaline Phosphates at Screening only	EOT, SAC
3.19.	Safety	LB17	Summary of Worst Case Chemistry Results by PCI Criteria Post-Baseline Relative to Baseline		EOT, SAC
Laboratory: Hematology					
3.20.	Safety	LB1	Summary of Hematology Data	For EOT summarise Eosinophils, Monocytes, Lymphocytes at Screening only	EOT, SAC
3.21.	Safety	LB1	Summary of Change from Baseline in Hematology	Only for WBC, lymphocytes, neutrophils	SAC
3.22.	Safety	LB17	Summary of Worst Case Hematology Results by PCI Criteria Post-Baseline Relative to Baseline		EOT, SAC
Laboratory: Hepatobiliary (Liver)					
3.23.	Safety	LIVER1	Summary of Liver Monitoring/Stopping Event Reporting		SAC
3.24.	Safety	LIVER10	Summary of Hepatobiliary Laboratory Abnormalities		SAC
ECG					
3.25.	Safety	EG1	Summary of ECG Findings	Include Worst Case Post-Baseline row	EOT, SAC
3.26.	Safety	EG2	Summary of ECG Values by Visit	For the following parameters: QTcF, QTcB, PR, Heart rate	EOT, SAC
3.27.	Safety	EG2	Summary of Change from Baseline in ECG Values by Visit	For the following parameters: QTcF, QTcB, PR, Heart rate	SAC
3.28.	Safety	Example 27	Summary of QTcF Categories		SAC
3.29.	Safety	Example 27	Summary of QTcB Categories		SAC

Safety: Tables					
No.	Population	IDSL / Example Shell	Title	Programming Notes	Deliverable [Priority]
3.30.	Safety	EG10	Summary of Maximum QTc Values Post-Baseline Relative to Baseline by Category		SAC
3.31.	Safety	EG11	Summary of Maximum Increase in QTc Values Post-Baseline Relative to Baseline by Category		SAC
3.32.	Safety	Example 25	Summary of ECG Abnormalities for Participants with Any Abnormal ECG Interpretation		EOT, SAC
Vital Signs					
3.33.	Safety	VS1	Summary of Vital Signs		SAC
3.34.	Safety	VS7	Summary of Worst Case Vital Signs Results by PCI Criteria Post-Baseline Relative to Baseline		EOT, SAC

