13.3. Appendix 3: Study Phases and Treatment Emergent Adverse Events

13.3.1. Study Periods

13.3.1.1. 12-Week Treatment Period

The 12-Week Treatment Period is assigned from Study Day 1 to Study Day 84.

13.3.1.2. 12-Week Follow-Up Period

The 12-Week Follow-up Period is assigned from Study Day 85 to Study Day 168.

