13.3.3. Treatment Emergent Flag for Adverse Events

Flag	Definition
Treatment Emergent	
 If AE onset date is on or after treatment start date & on or before treatment stop date plus 10 days.

NOTES:

- If the study treatment stop date is missing, then the AE will be considered to be On-Treatment.
- Time of study treatment dosing and start/stop time of AEs should be considered, if collected.

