13.11.4. Study Population Tables

Study Population Tables					
No.	Population	IDSL / Example Shell	Title	Programming Notes	Deliverable [Priority]
Subject Disposition					
1.1.	MITT	ES8	Summary of Subject Status and Reason for Study Withdrawal		EOT, SAC
1.2.	MITT	SD1	Summary of Treatment Status and Reasons for Discontinuation of Study Treatment		EOT, SAC
1.3.	APE	ES6	Summary of Screening Status and Reasons for Screen Failure		SAC
1.4.	APE	NS1	Summary of Number of Participants by Country and Site ID	For EOT, use MITT population and summarise country only: Summary of Number of Participants by Country	EOT, SAC
Protocol Deviation					
1.5.	MITT	DV1	Summary of Important Protocol Deviations		SAC
1.6.	MITT	IE1	Summary of Inclusion/Exclusion Criteria Deviations		SAC
Population Analysed					
1.7.	MITT	SP1	Summary of Study Populations		SAC
1.8.	MITT	SP2	Summary of Exclusions from the Per Protocol/Safety Population		SAC
Demographic and Baseline Characteristics					
1.9.	MITT	DM1	Summary of Demographic Characteristics	Use the following ranges for the Age Group row: ≤64; 65-74; ≥75	EOT, SAC
1.10.	APE	DM11	Summary of Age Ranges		SAC
1.11.	MITT	DM5	Summary of Race and Racial Combinations		SAC

Study Population Tables					
No.	Population	IDSL / Example Shell	Title	Programming Notes	Deliverable [Priority]
1.12.	MITT	MH4	Summary of Past Medical Conditions		SAC
1.13.	MITT	MH4	Summary of Current Medical Conditions		SAC
1.14.	MITT	FH1	Summary of Family History of Cardiovascular Risk Factors		SAC
1.15.	MITT	SU1	Summary of Smoking History at Screening		EOT, SAC
1.16.	MITT	SU1	Summary of Smoking Status Over the 12-Week Treatment Period		SAC
1.17.	MITT	SU1	Summary of Smoking Status Over the 12-Week Follow-Up Period		SAC
1.18.	MITT	Example 7	Summary of COPD Duration at Screening		SAC
1.19.	MITT	Example 1	Summary of COPD Exacerbation History at Screening	Use categories 0;1;2;3;≥3. Summarise moderate/severe, moderate; severe Include 7-Day History of COPD Exacerbations	EOT, SAC
1.20.	MITT	Example 1	Summary of COPD Exacerbation History at Screening by Country		SAC
Concomitant Medications					
1.21.	MITT	Example 14	Summary of Baseline COPD Maintenance Therapy	For EOT use categories: Triple, Non-triple	EOT, SAC
1.22.	MITT	Example 14	Summary of Baseline ICS Therapy	For EOT use categories: Yes, No	EOT, SAC
1.23.	MITT	Example 15	Summary of On-Treatment COPD Maintenance (Step-up) Therapy		SAC
1.24.	MITT	CM1	Summary of Concomitant Medications During 12-Week Treatment Period		SAC

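### The only general table of adverse events by maximum intensity (Table 3.6) covers all events, so no table shows general AE severity on drug by dose

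*SAP*

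**What the plan says.** Table and section numbers are those of the SAP version whose safety tables stand in Section 13.11.8. The other versions in the file have no intensity table, and that difference is not an error.

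- **Flag.** Section 13.3.3 defines an AE as treatment emergent as follows: "If AE onset date is on or after treatment start date & on or before treatment stop date plus 10 days".
- **Periods.** Section 13.3.1: "The 12-Week Treatment Period is assigned from Study Day 1 to Study Day 84" and "The 12-Week Follow-up Period is assigned from Study Day 85 to Study Day 168".
- **Tables that use the flag.** Table 3.1 is the "Summary of Treatment Emergent Adverse Events by System Organ Class and Preferred Term". Tables 3.3 to 3.5, 3.7 to 3.10, 3.13 and 3.14 are also titled as treatment emergent.
- **Tables for later events.** Table 3.2 is the "Summary of Post-Treatment Adverse Events by System Organ Class and Preferred Term", and Table 3.12 does the same for serious events.
- **Intensity.** Table 3.6 is the "Summary of All Adverse Events by Maximum Intensity by System Organ Class and Preferred Term". It uses the Safety population, is delivered at SAC only, and has an empty programming note. Section 8.1 refers only to the sponsor's core data standards, so the body text does not narrow it.
- **Discontinuation.** Table 3.11 is the "Summary of Adverse Events Leading to Permanent Discontinuation of Study Treatment or Withdrawal from Study by System Organ Class and Preferred Term". Listing 19 pools the same two outcomes.

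**The concern.** A maximum-intensity table takes one value per participant, the worst grade. If every recorded AE counts, a severe event well into follow-up can set that grade for someone who had only mild events on drug. The existing tables cannot undo this: 3.1 and 3.2 separate the periods but are not by intensity, and 3.6 is by intensity but does not separate the periods.

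This is a dose-ranging study with several active arms, so whether severe events rise with dose while participants take the drug is part of weighing the doses. Events that begin off drug and occur at a similar rate in all arms pull the arms towards each other in Table 3.6.

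**Working it through.** The plan states no figure here to reproduce. The check compares table scopes and then does window arithmetic.

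**1. Are off-drug events in the data?** Yes, by the SAP's own plan: Tables 3.2 and 3.12 exist to show them. How long they are collected is not stated. Two cases bracket it:
- to Day 168, the end of follow-up (Section 13.3.1);
- to Day 112, the last visit for vital signs, ECGs and laboratory tests (Section 2.1). That AE collection might also end there is an assumption.

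**2. Time outside the treatment-emergent window, Day 84 completer.**
- Window: 84 + 10 = 94 days.
- Collection to Day 168: 168 − 94 = 74 days; 74/168 = 44%.
- Collection to Day 112: 112 − 94 = 18 days; 18/112 = 16%.

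For early stoppers followed to Day 168 the share is larger. A stop on Day 56 gives (168 − 66)/168 = 102/168 = 61%; a stop on Day 28 gives (168 − 38)/168 = 130/168 = 77%.

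**3. Illustrative effect on a rate ratio.** The SAP gives no AE rates. Assume a constant hazard, with the off-window hazard in both arms equal to the placebo on-drug hazard. A true on-drug ratio R then appears as (94R + off-window days) / total days.

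| True R | To Day 168 | To Day 112 |
|---|---|---|
| 1.5 | (141 + 74)/168 = 1.28 | (141 + 18)/112 = 1.42 |
| 2.0 | (188 + 74)/168 = 1.56 | (188 + 18)/112 = 1.84 |

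**4. Effect on risks, which is what a per-participant table shows.** Under the same hazard assumption, with collection to Day 168, an on-drug risk p becomes q = 1 − (1 − p)(1 − p₀)^(74/94), where p₀ is the placebo on-drug risk.

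| On-drug risks (assumed) | Risks in an all-AE table | Risk ratio | Risk difference |
|---|---|---|---|
| 5% vs 10% | 8.8% vs 13.6% | 2.0 → 1.55 | 0.050 → 0.048 |
| 20% vs 40% | 32.9% vs 49.7% | 2.0 → 1.51 | 0.200 → 0.168 |

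Ratios move clearly towards 1. Differences hardly move when events are uncommon.

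**5. Table 3.11.** Stopping drug and leaving the study are pooled here, but they are reported separately elsewhere. Table 1.2 is the "Summary of Treatment Status and Reasons for Discontinuation of Study Treatment", Table 1.1 covers study withdrawal with reasons, and Listings 2 and 3 give the same split by participant. What no table gives is a system organ class and preferred term (SOC/PT) breakdown of AEs that led to stopping drug alone.

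**The case against.** The strongest reply is that nothing here is misstated. Table 3.6 is openly labelled as covering all events, and Section 13.3.3 does not require every AE table to use the flag. The serious, fatal, drug-related, common and special-interest tables are all treatment emergent. Table 3.6 is descriptive and comes only at SAC. The futility rules (Section 3.1.1.1) and the adaptation rule (Section 7.1.2) use FEV₁, exacerbation rate and design efficiency, and the internal safety committee reviews unblinded safety data throughout. All of that stands, and it limits the consequence. It does not supply a table of general AE severity on drug.

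The size is also open to challenge. The 44% needs AE collection to Day 168, which the SAP does not state. The hazard may not be constant in participants enrolled during an acute exacerbation; if events cluster early, dilution is smaller. Both points stand, so the ratios above are illustrations.

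A reader might infer three stronger things that the document does not support:

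- *That the plan has no on-drug severity display at all.* Post-inhalation cough, an event of special interest, has its own severity summaries at dosing visits (Section 8.1.1.1, Tables 3.15 to 3.17). The gap concerns AEs in general.
- *That drug discontinuation due to AEs cannot be seen, or is heavily diluted in Table 3.11.* Tables 1.1 and 1.2 separate the two outcomes with reasons, although the reason categories are not printed in the SAP. An AE that stops study drug will normally begin on drug, so only later study withdrawals could dilute the table, and the SAP gives no basis for sizing them.
- *That Table 3.6 cannot be related to Table 3.1.* Tables 3.1 and 3.2 and Listing 13 (all AEs) allow the events to be traced. The summary by grade and period is what is absent.

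**Conclusion.** The concern holds in a limited form. Table 3.6 is the only general AE table by intensity and is not restricted to treatment-emergent events, so a grade reached off drug can stand as a participant's maximum and no table shows general AE severity on drug by dose.

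For completers the off-window share is 16% to 44% of observed time, depending on a collection period that the SAP does not state. Any attenuation falls mainly on ratios, and its actual size cannot be derived from the SAP. This is a cheap improvement to one descriptive table; it neither contradicts the rest of the plan nor threatens a stated decision rule. The Table 3.11 point is secondary: only the SOC/PT breakdown for drug discontinuation alone is missing.

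**What to change.** Program and title Table 3.6 as *Treatment Emergent Adverse Events by Maximum Intensity*, using the Section 13.3.3 flag, or keep the all-AE table and add that version beside it. Optionally, split Table 3.11 into AEs leading to permanent discontinuation of study treatment and AEs leading to withdrawal from the study, each by system organ class and preferred term.

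The cost is one filter and a retitle, or one extra table, for Table 3.6, and one extra table if 3.11 is split. The flag already exists and no data collection changes.

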13.11.9. Safety Figures

Safety: Figures					
No.	Population	IDSL / Example Shell	Title	Programming Notes	Deliverable [Priority]
Laboratory					
3.1.	Safety	LB7	LFT Shift from Baseline to Maximum		EOT, SAC
3.2.	Safety	Example 34	Plot of Laboratory Data at Screening		EOT, SAC
3.3.	Safety	Example 13	Median (range) Absolute Neutrophil Count by Time and Treatment		SAC
ECG					
3.4.	Safety	EG8	Distribution of QTcF Change by Time and Treatment		SAC

13.11.10. Pharmacokinetic Tables

Pharmacokinetic: Tables					
No.	Population	IDSL / Example Shell	Title	Programming Notes	Deliverable [Priority]
Pharmacokinetic Concentration-Time Data					
4.1.	PK	PK01	Summary of Plasma GSK2269557 Pharmacokinetic Concentration-Time Data		SAC
4.2.	PK	PK05	Summary of Log-Transformed Plasma GSK2269557 Pharmacokinetic Concentration-Time Data		SAC

13.11.11. ICH Listings

ICH: Listings					
No.	Population	IDSL / Example Shell	Title	Programming Notes	Deliverable [Priority]
Subject Disposition					
1.	APE	ES7	Listing of Reasons for Screen Failure		SAC
2.	MITT	ES2	Listing of Reasons for Study Withdrawal		SAC
3.	MITT	SD2	Listing of Reasons for Study Treatment Discontinuation		SAC
4.	MITT	BL1	Listing of Participants for Whom the Treatment Blind was Broken		SAC
5.	MITT	TA1	Listing of Planned and Actual Treatments		SAC
Protocol Deviations					
6.	MITT	DV2	Listing of Important Protocol Deviations		SAC
7.	MITT	IE3	Listing of Participants with Inclusion/Exclusion Criteria Deviations		SAC
Populations Analysed					
8.	MITT	SP3	Listing of Participants Excluded from Per Protocol Population	For participants excluded from MITT population (i.e. participants in the MITT but not in PP)	SAC
Demographic and Baseline Characteristics					
9.	MITT	DM2	Listing of Demographic Characteristics		SAC
10.	MITT	DM9	Listing of Race		SAC
Prior and Concomitant Medications					
11.	MITT	CP_CM3	Listing of Concomitant Medications		SAC

ICH: Listings					
No.	Population	IDSL / Example Shell	Title	Programming Notes	Deliverable [Priority]
Exposure and Treatment Compliance					
12.	Safety	EX3	Listing of Exposure Data		SAC
Adverse Events					
13.	Safety	AE8	Listing of All Adverse Events		SAC
14.	Safety	AE7	Listing of Subject Numbers for Individual Adverse Events		SAC
15.	Safety	AE2	Listing of Relationship Between Adverse Event System Organ Classes, Preferred Terms, and Verbatim Text		SAC
Serious and Other Significant Adverse Events					
16.	Safety	AE8	Listing of Fatal Serious Adverse Events		SAC
17.	Safety	AE8	Listing of Non-Fatal Serious Adverse Events		SAC
18.	Safety	AE14	Listing of Reasons for Considering as a Serious Adverse Event		SAC
19.	Safety	AE8	Listing of Adverse Events Leading to Withdrawal from Study / Permanent Discontinuation of Study Treatment		SAC
Hepatobiliary (Liver)					
20.	Safety	MH2	Listing of Medical Conditions for Participants with Liver Stopping Events		SAC
21.	Safety	SU2	Listing of Substance Use for Participants with Liver Stopping Events		SAC
All Laboratory					
22.	Safety	LB5	Listing of All Chemistry Data for Participants with Any Value of Potential Clinical Importance		SAC
23.	Safety	LB14	Listing of Chemistry Data with Character Results		SAC

ICH: Listings					
No.	Population	IDSL / Example Shell	Title	Programming Notes	Deliverable [Priority]
24.	Safety	LB5	Listing of All Hematology Data for Participants with Any Value of Potential Clinical Importance		SAC
25.	Safety	LB14	Listing of all Hematology Data with Character Results		SAC
ECG					
26.	Safety	EG3	Listing of All ECG Values for Participants with Any Value of Potential Clinical Importance		SAC
27.	Safety	EG5	Listing of All ECG Findings for Participants with an Abnormal Finding		SAC

13.11.12. Non-ICH Listings

Non-ICH: Listings					
No.	Population	IDSL / Example Shell	Title	Programming Notes	Deliverable [Priority]
28.	MITT	Example 29	Listing of Subjects who Received Incorrect Medication		SAC
29.	PK	PK07	Listing of Plasma Pharmacokinetic Concentration-Time Data		SAC
30.	Safety	EG5	Listing of All ECG Findings for Subjects with an Abnormal Finding		SAC

13.12. Appendix 12: Example Mock Shells for Data Displays

13.12.1. Example shell 1

Example Shell X
Protocol: XYZ100001
Population: Intent-to-Treat/Safety/Other study specific

Page 1 of 1

Table X
Summary of COPD Exacerbation History at Screening

	Treatment A (N=100)	Treatment B (N=100)	Total (N=200)

Moderate COPD exacerbations			
n	X	X	X
0	xx (x%)	xx (x%)	xx (x%)
1	xx (x%)	xx (x%)	xx (x%)
>=2	xx (x%)	xx (x%)	xx (x%)
Severe COPD exacerbations			
n	X	X	X
0	xx (x%)	xx (x%)	xx (x%)
1	xx (x%)	xx (x%)	xx (x%)
>=2	xx (x%)	xx (x%)	xx (x%)
Total number of moderate/severe COPD exacerbations			
n	911	899	1810
0	313 (34%)	317 (35%)	630 (35%)
1	252 (28%)	253 (28%)	505 (28%)
>=2	346 (38%)	329 (37%)	675 (37%)

Note: Number of COPD exacerbations reported in the 12 months prior to the Screening Visit.

PPD

13.12.2. Example Shell 2

Protocol: XYZ100001

Page 1 of 1

Population: Intent-to-Treat/Safety/Other study specific

Table X
Summary of Treatment Compliance

	Treatment A (N=100)	Treatment B (N=100)	Total (N=200)

Overall compliance (%)			
n	xx	xx	xx
Mean	xx	xx	xx
SD	xx	xx	xx
Median	xx	xx	xx
Min.	xx	xx	xx
Max.	xx	xx	xx
Compliance interval			
< 80%	xx (x%)	xx (x%)	xx (x%)
80% - < 100%	xx (x%)	xx (x%)	xx (x%)
100% - < 120%	xx (x%)	xx (x%)	xx (x%)
>=120%	xx (x%)	xx (x%)	xx (x%)

PPD

13.12.3. Example shell 3

Example Shell X
Protocol: ABC123456
Population: Intent-to-Treat/Safety/Other study specific

Page 1 of n

Table X
Summary of Change from Baseline in FEV1 (L)
Measured post-bronchodilator

Visit	N	Treatment Arm	n	Mean	SD	Median	Min.	Max.
Day 1	200	Placebo	200	0.111	0.1111	0.100	-0.11	1.11
	200	GSK2269557 12.5 mcg	190	0.222	0.2222	0.200	-0.22	1.22
	200	GSK2269557 50 mcg	195	0.333	0.3333	0.300	-0.33	1.33
	200	GSK2269557 100 mcg	195	0.444	0.4444	0.400	-0.44	1.44
	200	GSK2269557 250 mcg	190	0.555	0.5555	0.500	-0.55	1.55
	200	GSK2269557 500 mcg	190	0.555	0.5555	0.500	-0.55	1.55
	200	GSK2269557 750 mcg	190	0.555	0.5555	0.500	-0.55	1.55
Day 14	200	Placebo	200	0.111	0.1111	0.100	-0.11	1.11
	200	GSK2269557 12.5 mcg	190	0.222	0.2222	0.200	-0.22	1.22
	200	GSK2269557 50 mcg	195	0.333	0.3333	0.300	-0.33	1.33
	200	GSK2269557 250 mcg	195	0.444	0.4444	0.400	-0.44	1.44
	200	GSK2269557 500 mcg	190	0.555	0.5555	0.500	-0.55	1.55
	200	GSK2269557 750 mcg	190	0.555	0.5555	0.500	-0.55	1.55

PPD

13.12.4. Example Shell 4

[figure not shown]
Protocol: ABC123456

Page 1 of 1

Population: Intent-to-Treat/Safety/Other study specific

Figure X

Plot of Number of Exacerbations in Previous 12 Months
(Moderate/Severe)

PPD

Protocol: ABC123456

Page 2 of 2

Population: Intent-to-Treat/Safety/Other study specific

Table X
Statistical Analysis of Change from Baseline in FEV1 (ml)
Measured post-bronchodilator

Visit	Treatment Comparison	Adjusted Median Difference	Std Dev	95% Credible Interval	Prob Treat. Diff >0 (%)
Day 14	GSK2269557 12.5 mg vs Placebo	x.xx	x.xx	(x.xx, x.xx)	x.xx
	GSK2269557 50 mg vs Placebo	x.xx	x.xx	(x.xx, x.xx)	x.xx
	GSK2269557 100 mg vs Placebo	x.xx	x.xx	(x.xx, x.xx)	x.xx
	GSK2269557 250 mg vs Placebo	x.xx	x.xx	(x.xx, x.xx)	x.xx
	GSK2269557 500 mg vs Placebo	x.xx	x.xx	(x.xx, x.xx)	x.xx
	GSK2269557 750 mg vs Placebo	x.xx	x.xx	(x.xx, x.xx)	x.xx
Day 28	GSK2269557 12.5 mg vs Placebo	x.xx	x.xx	(x.xx, x.xx)	x.xx
	GSK2269557 50 mg vs Placebo	x.xx	x.xx	(x.xx, x.xx)	x.xx
	GSK2269557 100 mg vs Placebo	x.xx	x.xx	(x.xx, x.xx)	x.xx

PPD

13.12.5. Example Shell 5

Protocol: ABC123456

Page 1 of 1

Population: Intent-to-Treat/Safety/Other study specific

Table X

Summary of On-treatment Exacerbations

	Treatment A (N=100)	Treatment B (N=100)

Number of moderate/severe exacerbations per subject		
0	50 (50%)	98 (98%)
1	6 (6%)	15 (15%)
2	6 (6%)	9 (9%)
3	1 (1%)	1 (1%)
4	0	2 (2%)
5	0	1 (1%)
>5	0	1 (1%)
Subjects with >=1 moderate/severe exacerbation	13 (13%)	28 (28%)
Total Number of moderate/severe exacerbations	21	49
Number of moderate exacerbations per Subject		
0	50 (50%)	98 (98%)
1	6 (6%)	15 (15%)
2	6 (6%)	9 (9%)
3	1 (1%)	1 (1%)

PPD

13.12.6. Example Shell 6

Protocol: ABC123456

Page 1 of 1

Population: Intent-to-Treat/Safety/Other study specific

Table X

Statistical Analysis of On-treatment Exacerbations

	Treatment A (N=100)	Treatment B (N=100)

Moderate/severe exacerbations		
Annual exacerbation rate (95% CrI)	0.35 (x.xx, x.xx)	0.30 (x.xx, x.xx)
Active vs. Placebo		
Ratio		0.85 (x.xx, x.xx)
Pr Diff <1		x.xx
Percent reduction in rate (95% CrI)		15% (x.xx, x.xx)
Predictive probability (%) [1]	xx%	
[only when required]		
Moderate exacerbations		
Annual exacerbation rate (95% CrI)	0.35 (x.xx, x.xx)	0.30 (x.xx, x.xx)
Active vs. Placebo		
Ratio		0.85 (x.xx, x.xx)
Pr Diff <1		x.xx
Percent reduction in rate (95% CrI)		15% (x.xx, x.xx)

[1] Predictive posterior probability of success at end of study, where success is $\Pr(\text{Reduction} > 0\%) > 80\%$

PPD

13.12.7. Example Shell 7

Protocol: ABC123456

Page 1 of 1

Population: Intent-to-Treat/Safety/Other study specific

Table X

Summary of COPD Duration at Screening

	Treatment A (N=100)		Treatment B (N=100)		Total (N=200)	
Duration of COPD:						
n	100		99		199	
<1 year	XX	(x%)	XX	(x%)	XX	(x%)
>=1 to <5 years	XX	(x%)	XX	(x%)	XX	(x%)
>=5 to <10 years	XX	(x%)	XX	(x%)	XX	(x%)
>=10 to <15 years	XX	(x%)	XX	(x%)	XX	(x%)
>=15 to <20 years	XX	(x%)	XX	(x%)	XX	(x%)
>=20 to <25 years	XX	(x%)	XX	(x%)	XX	(x%)
>=25 years	XX	(x%)	XX	(x%)	XX	(x%)

13.12.8. Example Shell 8

Protocol: ABC123456

Page 1 of 1

Population: Intent-to-Treat/Safety/Other study specific
Table X

Summary and Analysis of Time to Next On-treatment Moderate/Severe Exacerbation (days)
up to Day 84

	Treatment A (N=100)	Treatment B (N=100)
Number of Subjects with Event	10 (10%)	14 (14%)
Number of Subjects Censored	90 (90%)	86 (86%)
Treatment A vs. Placebo		
Hazard Ratio	X.XX	
95% Credible Interval	(x.xx, x.xx)	

Note: Hazard ratio and 95% Credible Interval are from a Bayesian Cox proportional hazards model

PPD

13.12.9. Example Shell 9

Protocol: ABC123456

Page 1 of 1

Population: Intent-to-Treat/Safety/Other study specific

Table X

Statistical Analysis of Proportion of Participants Achieving EXACT-definition of Response

	Treatment A (N=100)	Treatment B (N=100)

Day 14		
n	x.xx	x.xx
Responder	x.xx (x%)	x.xx (x%)
Non-responder	x.xx (x%)	x.xx (x%)
Active vs. Placebo		
Odds Ratio (OR) (95% CrI)	x.xx (x.xx, x.xx)	x.xx (x.xx, x.xx)
Pr OR >1	x.xx	x.xx
Day 28		
n	x.xx	x.xx
Responder	x.xx (x%)	x.xx (x%)
Non-responder	x.xx (x%)	x.xx (x%)
Active vs. Placebo		
Odds Ratio (95% CrI)	x.xx (x.xx, x.xx)	x.xx (x.xx, x.xx)
Pr Diff >1	x.xx	x.xx

PPD

13.12.10. Example Shell 10

Protocol: XYZ100001

Page 1 of n

Population: Intent-to-Treat/Safety/Other study specific

Table X

Summary of severity of subsequent HCRU-defined exacerbation during 12-Week Treatment Period

Treatment	N	n	Mean	SD	Median	Min.	Max.
Placebo	30	30	xx.xx	xx.xx	xx.xx	xx.xx	xx.xx
Trt A	30	30	xx.xx	xx.xx	xx.xx	xx.xx	xx.xx
Trt B	30	30	xx.xx	xx.xx	xx.xx	xx.xx	xx.xx

PPD

13.12.11. Example Shell 11

Protocol: ABC123456

Page 1 of 1

Population: Intent-to-Treat/Safety/Other study specific

Table X

Mixed Model Repeated Measures Analysis of CAT Total Score

	Treatment A (N=100)	Treatment B (N=100)

Day 28		
n	x.xx	x.xx
Adjusted mean score change (SE)	x.xx (x)	x.xx (x)
Active - Placebo		
Difference (SE)	x.xx (x.xx)	x.xx (x.xx)
95% (CrI)	x.xx	x.xx
Pr Diff >0	x.xx	x.xx
Day 56		
n	x.xx	x.xx
Adjusted mean score change (SE)	x.xx (x)	x.xx (x)
Active - Placebo		
Difference (SE)	x.xx (x.xx)	x.xx (x.xx)
95% (CrI)	x.xx	x.xx
Pr Diff >0	x.xx	x.xx

13.12.12. Example Shell 12

Protocol: ABC123456

Page 1 of 1

Population: Intent-to-Treat/Safety/Other study specific

Table X
Summary of the Number of Subsequent (On-treatment) Exacerbations Treated with Steroids/Antibiotics

	Treatment A (N=100)	Treatment B (N=100)
Total exacerbations	50	51
Treatment		
Antibiotics	30	40
Steroids	50	40
Both	30	30

[figure not shown]
PPD

13.12.13. Example shell 13

Protocol: XYZ100001
Population: Intent-to-Treat/Safety/Other study specific

Page 1 of 1

Figure X
Median (range) Absolute Neutrophil Count by Time and Treatment

PPD

13.12.14. Example Shell 14

Protocol: XYZ100001

Page 1 of n

Population: Intent-to-Treat/Safety/Other study specific

Table X
Summary of Baseline COPD Maintenance Therapy

Therapy category	Treatment A (N=81)	Treatment B (N=79)
Any medication at baseline	70 (86%)	50 (63%)
Monotherapy	X (x%)	X (x%)
LAMA only	x (x%)	x (x%)
Dual therapy	x (x%)	x (x%)
ICS/LABA	x (x%)	x (x%)
Dual bronchodilator	xx (xx%)	xx (xx%)
Triple therapy	X (x%)	X (x%)
LAMA/ICS/LABA	x (x%)	0

PPD

13.12.15. Example Shell 15

Protocol: XYZ100001

Population: Intent-to-Treat/Safety/Other study specific

Page 1 of n

Table X
Summary of On-Treatment COPD Maintenance (Step-up) Therapy

Therapy category	Treatment A (N=81)	Treatment B (N=79)
Any Step-up Therapy	70 (86%)	50 (63%)

PPD

13.12.16. Example shell 16

Protocol: XYZ100001

Page 1 of n

Population: Intent-to-Treat/Safety/Other study specific

Table X
Summary of OCS use

	Treatment A (N=81)	Treatment B (N=79)
OCS use for index exacerbation	81 (100%)	79 (100%)
Total number of Days of OCS use		
Mean	Xx	xx
SD	Xx	xx
Median	Xx	xx
Min.	Xx	xx
Max.	Xx	xx
On-treatment OCS use	xx (xx%)	xx (xx%)
Total number of Days of OCS use		
Mean	Xx	xx
SD	Xx	xx
Median	Xx	xx
Min.	Xx	xx
Max.	Xx	xx

PPD

13.12.17. Example Shell 17

Protocol: ABC123456
Population: Safety

Page 1 of x

Table X
Summary of Post-Inhalation Cough by Visit

Visit: VISIT 2 (RANDOMISATION)

	Placebo (N=43)	GSK2269557 50 mcg (N=14)	GSK2269557 100 mcg (N=15)	GSK2269557 250 mcg (N=16)	GSK2269557 500 mcg (N=14)	GSK2269557 750 mcg (N=42)
Did subject experience PI cough? [1]						
n	20	10	12	15	12	35
Yes	7 (35%)	4 (40%)	6 (50%)	3 (20%)	6 (50%)	12 (34%)
No	13 (65%)	6 (60%)	6 (50%)	12 (80%)	6 (50%)	23 (66%)
Type of cough						
Single cough	4 (57%)	2 (50%)	1 (17%)	1 (33%)	1 (17%)	2 (17%)
Intermittent cough	2 (29%)	2 (50%)	5 (83%)	1 (33%)	4 (67%)	5 (42%)
Continuous cough	1 (14%)	0	0	1 (33%)	1 (17%)	5 (42%)
Severity of cough						
Mild	5 (71%)	3 (75%)	3 (50%)	2 (67%)	1 (17%)	6 (50%)
Moderate	2 (29%)	1 (25%)	2 (33%)	1 (33%)	5 (83%)	4 (33%)
Severe	0	0	1 (17%)	0	0	2 (17%)
Time to onset of PI cough (minutes)						
0-1	6 (86%)	3 (75%)	6 (100%)	3 (100%)	6 (100%)	12 (100%)
>1-2	1 (14%)	1 (25%)	0	0	0	0
>2-3	0	0	0	0	0	0
>3-4	0	0	0	0	0	0
>4-5	0	0	0	0	0	0
>5	0	0	0	0	0	0
Duration of PI cough (minutes)						
<=1	6 (86%)	3 (75%)	5 (83%)	3 (100%)	5 (83%)	11 (92%)
>1-2	1 (14%)	1 (25%)	1 (17%)	0	1 (17%)	1 (8%)
>2-3	0	0	0	0	0	0
>3-4	0	0	0	0	0	0
>4-5	0	0	0	0	0	0

>5-10	x		x					
>10-30	x		x					
>30	x		x					
Number of subjects reporting cough as								
AE/SAE	2	(29%)	1	(25%)	4	(67%)	0	
Mild	x	(x%)	x				2	(33%)
Moderate	x	(x%)	x					
Severe	x	(x%)	x				3	(25%)

[1] Percentages are calculated using the number of subjects evaluated at visit as the denominator.
All other percentages are calculated using the number of subjects with a PI cough at visit as the denominator.

13.12.18. Example shell 18

[figure not shown]
Protocol: ABC123456

Page 1 of x

Population: Intent-to-Treat/Safety/Other study specific

Figure X

Plot of Dose Response Model of Change from Baseline in FEV1

[Footnote to describe the fitted model]

PPD

13.12.19. Example Shell 19

Protocol: ABC123456

Page 1 of 3

Population: Intent-to-Treat/Safety/Other study specific
Table X

Summary of COPD Related Unscheduled Healthcare Resource Utilization

		Treatment A (N=100)	Treatment B (N=100)
Unscheduled Healthcare Utilisation	Yes	97 (97%)	19 (19%)
	No	3 (3%)	81 (81%)
Number of Home Visits (day)	n	100	100
	0	90 (90%)	92 (92%)
	1	4 (4%)	4 (4%)
	2	0	0
	3	0	0
	>3	0	2 (<1%)
	Total [1]	4	4
Number of Home Visits (night)	n	100	100
	0	100 (100%)	100 (100%)
	1	0	0
	2	0	0
	3	0	0
	>3	0	0
	Total [1]	0	0

[1] Total number of contacts across all subjects.

[2] Total number of days across all subjects.

PPD

Protocol: ABC123456

Page 2 of 3

Population: Intent-to-Treat/Safety/Other study specific

Table X

Summary of COPD Related Unscheduled Healthcare Resource Utilization

		Treatment A (N=100)	Treatment B (N=100)

Number of Office/Practice Visits	n	911	899
	0	846 (93%)	808 (90%)
	1	42 (5%)	58 (6%)
	2	13 (1%)	23 (3%)
	3	7 (<1%)	8 (<1%)
	>3	3 (<1%)	2 (<1%)
	Total [1]	103	140
Number of Urgent Care/Outpatient Visits	n	911	899
	0	886 (97%)	882 (98%)
	1	15 (2%)	10 (1%)
	2	3 (<1%)	2 (<1%)
	3	3 (<1%)	3 (<1%)
	>3	4 (<1%)	2 (<1%)
	Total [1]	54	37
Number of Emergency Room Visits	n	911	899
	0	906 (>99%)	893 (>99%)
	1	5 (<1%)	5 (<1%)
	2	0	1 (<1%)
	3	0	0
	>3	0	0
	Total [1]	5	7

[1] Total number of contacts across all subjects.

[2] Total number of days across all subjects.

PPD

Protocol: ABC123456

Page 3 of 3

Population: Intent-to-Treat/Safety/Other study specific

Table X

Summary of COPD Related Unscheduled Healthcare Resource Utilization

		Treatment A (N=100)	Treatment B (N=100)

Number of Days in Intensive Care	n	911	899
	0	910 (>99%)	894 (>99%)
	1	0	0
	2	0	1 (<1%)
	3	0	0
	>3	1 (<1%)	4 (<1%)
	Total [2]	12	40
Number of Days in General Ward	n	911	899
	0	896 (98%)	878 (98%)
	1	0	2 (<1%)
	2	1 (<1%)	1 (<1%)
	3	0	0
	>3	14 (2%)	18 (2%)
	Total [2]	119	258

[1] Total number of contacts across all subjects.

[2] Total number of days across all subjects.

PPD

13.12.20. Example Shell 20

Protocol: ABC123456

Page 1 of x

Population: Intent-to-Treat/Safety/Other study specific
Table X

Summary of Non-COPD Related Unscheduled Healthcare Resource Utilization

		Treatment A (N=100)	Treatment B (N=100)
Unscheduled Healthcare Utilisation	Yes	97 (97%)	19 (19%)
	No	3 (3%)	81 (81%)
Number of Days in Accident and emergency	n	100	100
	0	90 (90%)	92 (92%)
	1	4 (4%)	4 (4%)
	2	0	0
	3	0	0
	>3	0	2 (<1%)
	Total	4	4
Number of Days in General Ward	n	100	100
	0	100 (100%)	100 (100%)
	1	0	0
	2	0	0
	3	0	0
	>3	0	0
	Total	0	0

PPD

13.12.21. Example Shell 21

Protocol: ABC123456

Page 1 of 1

Population: Intent-to-Treat/Safety/Other study specific

Table X

Summary of Exacerbation Related Hospitalizations

	Treatment A (N=100)	Treatment B (N=100)

Index exacerbation		
Participants with hospitalization	x.xx	x.xx
Number of hospitalizations	x.xx	x.xx
Mean duration (days)	x.xx	x.xx
SD	x.xx	x.xx
Median duration (days)	x.xx	x.xx
Minimum duration (days)	x.xx	x.xx
Maximum duration (days)	x.xx	x.xx
Subsequent exacerbations		
Participants with hospitalization	x.xx	x.xx
Number of hospitalizations	x.xx	x.xx
Mean duration (days)	x.xx	x.xx
SD	x.xx	x.xx
Median duration (days)	x.xx	x.xx
Minimum duration (days)	x.xx	x.xx
Maximum duration (days)	x.xx	x.xx

13.12.22. Example Shell 22

Protocol: ABC123456

Page 1 of 1

Population: Intent-to-Treat/Safety/Other study specific
Table X

Summary of Re-hospitalization Within 30 days of Index Exacerbation

		Treatment A (N=100)	Treatment B (N=100)
Re-hospitalization Within 30 days	Yes	97 (97%)	19 (19%)
	No	3 (3%)	81 (81%)

13.12.23. Example Shell 23

